5.2.1. Alcohol Biological Testing

Please follow the next steps when collecting biological samples.

1. Provide participant with a urine cup to collect a urine sample as part of the screening process.
2. Check the expiration dates when preparing the test.
3. Make sure you have a marker to label the test with the participant's study ID before you start the testing.

Remember, willingness to be tested for alcohol is a requirement for study participation. If a participant has difficulty to pass urine, encourage them to drink some water or juice continue with explanations or completing other forms and to provide the urine sample a bit later. Giving the participant a drink before she starts the appointment will also be helpful.

TEST INSTRUCTIONS

For this study, we will be using an EtG urine test to determine if someone has alcohol in their body. EtG stands for *ethyl glucuronide*, which is a substance produced in the liver when your body processes alcohol. EtG remains present in the body for about one to five days after drinking, depending on how much alcohol a person has drank, using small strips that are dipped in urine. Please use gloves before, during and while cleaning up after the biological testing process. Please conduct the testing as per the steps indicated.

Know What to Expect in 3 Easy Steps

Dip

Dip the dip card into the collected urine sample for 10 sec.

Wait

Re-cap the dip card and lay it on a flat, clean surface.

Read

Read the results at 5 min.

Record results on **MaRISA Specimen Collection Log**.

CLEANING AFTER TESTING

Make sure everything is thrown away appropriately after you have completed all biological testing. Everything used for the testing such as the tray must be wiped down with sanitizer or wipes after conducting biological tests.

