5.2. Screening

Once introductions are made and a patient's cooperation has been secured, complete the participant ID, staff ID, site and date fields on the screener, using the tablet.

- For the pilot phase, we will be using the "Pilot Screener for Pregnant and Post-Partum Women" at the onset of the pilot phase.

Recruitment will be done via clinic referrals, posters, and flyers.

Participant IDs will be according to the following format, it will consist of ten digits with both alphabetic and numerical items, e.g., M_BL0001PR or M_BL0001PP.

Please note: the first alphabetic digit refers to the MaRISA study, an underscore sign separates it from the next 2 alphabetic digits which indicates the site, e.g., Bishop Lavis = M_BL, the next 4 digits indicates how many participants have been enrolled into the study and the last 2 digits indicates whether the participant is currently pregnant or post-partum.

There are types of potentially sensitive information that are requested on the screening questionnaire. It is important to stress the confidential nature of the screener. Reassure them that their identity will never be linked to their responses and that their responses are only used for research purposes. Always remind individuals that their answers will be kept strictly confidential.

Staff ID#: Will be a staff member's Initials.

Site ID#: Bishop Lavis = M_BL; Macassar = 002

To be eligible, women must fulfil in the following criteria, i.e.:

Criterion	Participants
Age	Be ≥ 18
Pregnancy or Post-Partum Status	be pregnant (≤ 28 ges wks) or postpartum (≤ 3 mos)
Alcohol Use	
 have reported alcohol use during the current pregnancy or lactation test positive for alcohol use by urinalysis (i.e., EtG)
Birth Venue (linked to birth outcomes)	plan to complete antenatal care at the current clinic and remain in the area for at least 3 months
Cellphone Status	own a cell phone to receive text messages
Serious Medical Conditions and Suicidal Thoughts	women who report serious medical problems threatening their current pregnancy or report current suicidal thoughts or attempts in the past month are NOT eligible
Other	intend to breastfeed for 6 months

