5.4. Follow-up Appointments and reimbursements

The participant will be reimbursed for their transport costs based on the following scale. Transport costs should only be reimbursed if the participant has needed to travel to come to the healthcare facility for a study appointment:

Categories of distances	Amount provided
0km – 3km	R10
4km – 10km	R30
11km +	R50

Pilot Phase:

In addition to monitoring participants' through urinalysis twice a week, participants will be asked to participate in the 6-week and 3-month follow-up assessments at the healthcare facility they were enrolled at.

A participant will be provided R150.00 each at baseline and follow-up assessments.

Consent will be obtained to collect participants' birthing facility information for those who were recruited during pregnancy to track birth outcomes. If a participant is already postpartum and breastfeeding, self-reported incidents of breastfeeding while using alcohol will be collected. Infants' data relating to their height, weight, and head circumference will be collected.

If a participant misses a visit, we will contact the participant following a standard protocol (i.e., phone call on the appointment day, the following day, and 1 week after the missed visit to encourage rescheduling for the missed appointment). Participant locator information will also be updated at each appointment. Staff members need to

prioritize tracking participants who have the least number of days left before their upcoming appointment so that they do not time out of the study. In other words, you should contact participants first whose next appointment is closest to the current date.

If a participant has withdrawn from the study or has reported the loss of her foetus/baby to field staff and this was reported to Project Coordinator, the participant should not be tracked any longer. These participants will also not be replaced in the study since they have been reported on.

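### Protocol 5.2.1 favours a drink before the appointment, which can only lower the chance that a drinking woman tests EtG-positive at screening; the size of the effect is unknown

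*Protocol*

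**What the plan says.** Protocol 5.2.1 (Alcohol Biological Testing) gives two pieces of advice on fluids. The first is conditional: "If a participant has difficulty to pass urine, encourage them to drink some water or juice". The second has no stated condition: "Giving the participant a drink before she starts the appointment will also be helpful". Neither gives a volume or a time between drink and sample.

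The same section says "we will be using an EtG urine test to determine if someone has alcohol in their body". The card is dipped, read at 5 minutes, and the result is entered on the Specimen Collection Log. The section states no cut-off, no check for dilute urine and no repeat test. It puts detectability at about 1 to 5 days after drinking, depending on the amount.

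At entry, the eligibility table in 5.2 lists a positive EtG result under alcohol use, and the disposition table gives a negative EtG its own code, 2.02. After entry, 5.4 has women monitored "through urinalysis twice a week" but describes no collection procedure. The scope of 5.2.1 is mixed: it opens generally, "Please follow the next steps when collecting biological samples", but its first step reads "Provide participant with a urine cup to collect a urine sample as part of the screening process".

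The SAP tests change from baseline in variables related to alcohol use with the Cochran-Armitage trend test. It does not name EtG.

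**The concern.** A dip card read as positive or negative has some detection limit, whether or not the manual states it. Fluid taken shortly before sampling can lower the EtG concentration without any change in drinking. A woman well above the limit stays positive. A woman just above it can become negative.

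At screening this matters directly, because a negative card keeps a woman out even if she reports drinking. Those most exposed are light drinkers and women late in the detection window. Losing them slows recruitment to a 60-woman pilot and shifts the sample towards heavier or more recent drinking. How much fluid is given may also differ by fieldworker and site, so the screening test is not applied uniformly.

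There is a possible second effect. Women enter with a positive card, so any negative caused by dilution at a later visit would point towards reduced drinking. The SAP looks at change from baseline and describes no comparison group that would absorb such an error. This second effect depends on two things that the documents leave open.

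**Working it through.** **No plan figure to reproduce.** The documents give no cut-off, concentrations, drink volume or test sensitivity. The arithmetic below is an illustration on assumed inputs.

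**Inputs.** From the documents: 60 women planned (Chapter 5, introduction), positive EtG at entry (5.2), disposition 2.02, twice-weekly urinalysis (5.4). Assumed: EtG in drinking women is log-normal with median *m* times the cut-off, *m* = 2 to 10; SD on the natural-log scale *s* = 1 to 2; dilution factor *D* = 1.25 to 2, applied to every woman.

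**Formula.** P(positive) = Φ((ln *m* − ln *D*)/*s*). A sample changes from positive to negative when its undiluted concentration lies between 1 and *D* times the cut-off.

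Example, *m* = 2, *s* = 1: undiluted Φ(0.693) = 75.6%; at *D* = 2, Φ(0) = 50.0%; loss 25.6 points.

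| *m* | *s* | No dilution | *D* = 1.25 | *D* = 1.5 | *D* = 2 | Loss in points (1.25 / 1.5 / 2) |
|---|---|---|---|---|---|---|
| 2 | 1.0 | 75.6% | 68.1% | 61.3% | 50.0% | 7.5 / 14.3 / 25.6 |
| 2 | 1.5 | 67.8% | 62.3% | 57.6% | 50.0% | 5.5 / 10.2 / 17.8 |
| 2 | 2.0 | 63.6% | 59.3% | 55.7% | 50.0% | 4.3 / 7.9 / 13.6 |
| 5 | 1.0 | 94.6% | 91.7% | 88.6% | 82.0% | 2.9 / 6.0 / 12.6 |
| 5 | 1.5 | 85.8% | 82.2% | 78.9% | 72.9% | 3.6 / 6.9 / 12.9 |
| 5 | 2.0 | 79.0% | 75.6% | 72.6% | 67.7% | 3.4 / 6.4 / 11.3 |
| 10 | 1.0 | 98.9% | 98.1% | 97.1% | 94.6% | 0.8 / 1.8 / 4.3 |
| 10 | 1.5 | 93.8% | 91.7% | 89.7% | 85.8% | 2.1 / 4.1 / 8.0 |
| 10 | 2.0 | 87.5% | 85.1% | 82.9% | 79.0% | 2.4 / 4.6 / 8.5 |

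The loss runs from 0.8 to 25.6 points. If only a fraction *f* of women take the drink, it is multiplied by *f*.

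**Screening.** The number of drinking women to test for 60 positives is 60/P. At the high end (*m* = 2, *s* = 1, *D* = 2) it goes from 60/0.756 = 79 to 60/0.500 = 120. At the low end (*m* = 10, *s* = 1, *D* = 1.25) it goes from 60/0.989 = 60.7 to 60/0.981 = 61.2, less than one extra woman.

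**Monitoring, if 5.2.1 applies there.** Entry on a positive card means 100% positive at the start. Suppose nobody changes her drinking.

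- If each woman's concentration and dilution are the same at every visit, she stays positive and the later loss is zero.
- If concentrations are drawn afresh at each visit, positivity falls with no drink at all. Undiluted positivity is 63.6% to 98.9%, a fall of 1.1 to 36.4 points from selection alone. Dilution adds to that. For *m* = 2, *s* = 1, *D* = 2: 24.4 points from selection (0.244 × 60 = 14.6 women), then 25.6 from dilution (0.256 × 60 = 15.4 women). For *m* = 10, *s* = 1, *D* = 1.25: 1.1 points (0.7 women), then 0.8 (0.5 women).

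A later fall in positivity therefore cannot be put down to fluid as a whole.

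**The case against.** The strongest reply is that this is one advisory sentence in a field manual for a 60-woman pilot with a short, mainly descriptive SAP. The word used is helpful, not required. The sentence follows the advice on difficulty passing urine and can be read as part of it. That reading is possible, but a drink given before the appointment starts is, at least at screening, given before anyone knows whether the woman will have difficulty. As written, the sentence does not restrict itself.

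A reader might infer more than the documents support, and three such inferences should be set aside.

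- *That the monitoring samples are collected under the same advice.* Section 5.2.1 sits under Screening, its first step names screening, and 5.4 does not refer back to it. The extension is reasonable, since no other urine procedure is given, but it remains an inference.
- *That diluted negatives will be read as abstinence and will inflate the trial's result.* No section says how monitoring results are interpreted, and the SAP does not list EtG. The analysed alcohol variables could be the self-reported ones in 5.3. Part of any fall after entry also comes from enrolling only EtG-positive women, which a change to fluids would leave in place.
- *That fluid intake goes unrecorded and cannot be recovered.* The fields of the Specimen Collection Log are not in the documents. One can say only that the manual does not ask staff to record fluids.

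The objection that the size is unanchored also stands. The larger losses need a median close to the cut-off and a 2-fold dilution. One ordinary drink may do much less.

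These points do not remove the direction of the effect or its route to exclusion at screening.

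**Conclusion.** The point holds in a limited form that rests mainly on screening. Protocol 5.2.1 favours fluid before sampling, sets no limit on it and describes no check for dilute urine or repeat test, while a negative card excludes a woman. Following the advice can only lower the chance that a drinking woman tests positive.

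The size is not known. The range of about 1 to 26 points applies to unselected drinking women and depends entirely on the assumed median (2 to 10 times the cut-off), spread (log-SD 1 to 2) and dilution (1.25- to 2-fold in every woman). The lower end is plausible for a single drink.

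A contribution to apparent reduction after entry is conditional on two unstated matters: that 5.2.1 governs the twice-weekly samples, and that EtG is among the analysed alcohol variables. If both are true, dilution would add to the fall expected from positive-only entry. A correction is worth making because it is cheap and has to be in place before samples are taken.

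**What to change.** - In 5.2.1, delete the sentence on a drink before the appointment.
- Once screening begins, or on arrival at a monitoring visit, collect urine before any study-supplied drink or snack.
- Keep fluids for women who cannot pass urine. On the Specimen Collection Log, record the volume given (zero if none) and the time from drink to sample.
- State in 5.2.1 and 5.4 that the same order applies at screening and at every twice-weekly visit.
- In the SAP, say whether EtG is an analysed alcohol variable. Report EtG positivity with and without after-fluid samples as a sensitivity analysis only, since women who need fluid to pass urine may differ from the rest.

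The cost is one deleted sentence, short additions to the text, two log fields and slightly longer waits for some women. No new test or staff are needed. Fluid drunk before arrival stays uncontrolled, and the change does not detect dilute urine. It removes only the part that the study itself introduces. The fall that follows from enrolling only EtG-positive women also remains.

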5.3. Baseline Assessment

Remind the participant of their rights to confidentiality and privacy in answering the questions with the exception if they indicate desire to harm themselves or someone else. Refer to the Distressed Participant Procedures (see **Chapter 6**) if a patient ever indicates they will do harm to themselves or someone else. If the participant has any questions or concerns about being in the study, they can contact the Site PI. Her contact information is on the **Information and Consent Form**.

Baseline assessment questions will be conducted via CASI on a tablet. Assessment questions will cover sociodemographic factors; social determinants; recent and lifetime polysubstance and alcohol use; IPV/GBV exposure; partner drinking; stigma; coping with stress; and reproductive, sexual, physical, and mental health.

5.4. Follow-up Appointments and reimbursements

The participant will be reimbursed for their transport costs based on the following scale. Transport costs should only be reimbursed if the participant has needed to travel to come to the healthcare facility for a study appointment:

Categories of distances	Amount provided
0km – 3km	R10
4km – 10km	R30
11km +	R50

Pilot Phase:

In addition to monitoring participants' through urinalysis twice a week, participants will be asked to participate in the 6-week and 3-month follow-up assessments at the healthcare facility they were enrolled at.

A participant will be provided R150.00 each at baseline and follow-up assessments.

Consent will be obtained to collect participants' birthing facility information for those who were recruited during pregnancy to track birth outcomes. If a participant is already postpartum and breastfeeding, self-reported incidents of breastfeeding while using alcohol will be collected. Infants' data relating to their height, weight, and head circumference will be collected.

If a participant misses a visit, we will contact the participant following a standard protocol (i.e., phone call on the appointment day, the following day, and 1 week after the missed visit to encourage rescheduling for the missed appointment). Participant locator information will also be updated at each appointment. Staff members need to

prioritize tracking participants who have the least number of days left before their upcoming appointment so that they do not time out of the study. In other words, you should contact participants first whose next appointment is closest to the current date.

If a participant has withdrawn from the study or has reported the loss of her foetus/baby to field staff and this was reported to Project Coordinator, the participant should not be tracked any longer. These participants will also not be replaced in the study since they have been reported on.

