2.2. Roles and Responsibilities of Staff

2.2.1 Organogram

2.2.2 Project Staffing

There are a variety of staff working on this project.

Project Coordinator: is responsible for assisting the Site-PI with all study related activities and co-ordination, including applications for approval to the Department of Health. They are responsible for overseeing day-to-day activities, ensuring that all study-related materials and incentives are available. They are responsible for data management and will provide support in the reproduction of study-related materials, and assist with literature searches, preparation of slides and other materials for reports, presentations, and publications. They are supervising all field workers, provide training to field workers on recruitment, data collection and tracking procedures. They will conduct quality checking to ensure all data storage SOPs and data collection SOPs are being adhered to. This will include collection of self-report and biological data. They will be responsible for maintaining regulatory (GCP and ethics) oversight, maintenance and stock control of supplies.

Fieldworkers

Will be based at the participating healthcare facilities and MOUs. They will be responsible for conducting screening to identify potential patients who are eligible to participate in the study, consenting eligible patients and enrolling them in the study, scheduling appointments, collecting contact information, conducting the baseline and follow up assessments and tracking participants for study appointments. All of these activities will require the completion of certain paperwork that will be explained in subsequent chapters of this manual. When conducting such activities, staff members must be very conscientious about checking the quality of their own work and ensuring that all interviews are completely and accurately documented using the appropriate forms. Fieldworkers will report directly to the Project Coordinator and indirectly to the Site PI.

Fieldworkers Daily Tasks:

- Maintain confidentiality at all times,
- Be flexible with scheduling appointments (e.g., late afternoon appointments or weekend follow up appointments for assessments),
- Check the quality of own work,
- Check email accounts at least once daily,
- Check project-device messages regularly throughout the day,
- Maintain appointment book
- Keep all supplies in a secure location,
- Report any missing items immediately to the Project Coordinator and

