7.1.1. Adverse Events (AE)

Adverse Events (AEs) will be defined as: report of coercion to participate in the study; or significant hesitation, concern or emotional distress from answering research, such that the participant decides to stop their participation; and harm resulting from breach of confidentiality. Medical events for postpartum health, psychiatric issues including suicidal ideation, or substance abuse that do not require urgent medical attention, emergency care, and/or hospitalization will be also treated as AEs. We will monitor attrition rates for participants but drop out from the study will not be reported as an AE unless it is decided to be related to an untoward event from study participation. Clinically insignificant events are not considered AE's. Examples of clinically insignificant events include mild viral illness (e.g., colds, flu, and runny nose), common headaches, minor scratches, and mild symptoms or problems associated with medical conditions not related to the postpartum periods. As per the definition of AEs, only significant worsening of baseline medical or psychiatric status or new problems will be reported as AEs.

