SAEs (e.g., death or hospitalization) will be reported within 24 - 48 hours of their occurrence by the Site PI, the PI, the SAMRC Research Ethics Committee, and our NIAAA project officer. SAEs will be reported regardless of whether they are considered to be study related. SAEs will be systematically assessed by staff at each participant contact as well as at each scheduled follow-up. At each follow-up, all research participants will be asked whether they had been hospitalized overnight in the past 30 days. In the event that a participant either withdraws from the study or the investigator decides to discontinue a participant due to an SAE, the participant will be monitored by the investigator via ongoing status assessment until (1) a resolution is reached (the problem requiring hospitalization has resolved or stabilized with no further changes expected), (2) the SAE is determined to be clearly unrelated to the study intervention, or (3) the SAE results in death. The PI will review the study protocol with other senior research staff and/or the ethics committee and determine what further action to take based on the best interests of the participants and of the research. With input from the PI, the SAMRC Research Ethics Committee may recommend continuation of the study, modifications to the study, or termination of the study if unacceptable.

Event	Description	Example	Reporting Requirements/Actions
Community/ Environmental Report	Any incident in which events in the community/study environment directly or indirectly have a time/cost/quality effect on the study progress. These incidents are either observed, reported in the media or information obtained from community members	Fires/Floods, natural disasters, taxi violence, service delivery strikes, development of RDP housing (temporary zone restructure resulting in community member migration), political activity, study team excluded from a community due to protest against the study	Reporting to: Project Coordinator Senior Management: PI & Site PI
Staff Safety Incident	Incidents in which staff or any other person are threatened	A participant or any other individual	Reporting to: Project Coordinator

		becomes violent towards a staff	Senior Management: PI & Site PI
Participant Harms			

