Maternal Alcohol Reduction Intervention in South Africa [MaRISA]

NCT05319977; May 18, 2021

Descriptive statistics will be used to describe the data for the overall sample and separately for participants enrolled while pregnant and postpartum. Data will be summarized using the mean (standard deviations) for continuous variables and percentages (frequency) for categorical variables. Changes from baseline to follow-up assessments on variables related to alcohol use and contextual/co-occurring issues (i.e., violence and depression) will be evaluated using the Cochran-Armitage Trend test. All analyses will be performed using SAS version 9.4.

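### Does ending tracking after the loss of a foetus or baby leave the baseline-to-follow-up comparison without a rule it needs?

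*Protocol*

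**What the plan says.** Protocol section 5.4 treats two groups alike: women who withdraw, and women with a reported loss. For the second, the text is that if a participant has "reported the loss of her foetus/baby to field staff and this was reported to Project Coordinator, the participant should not be tracked any longer". It adds: "These participants will also not be replaced in the study since they have been reported on".

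Tracking is appointment work. Section 2.2.2 makes fieldworkers responsible for "conducting the baseline and follow up assessments and tracking participants for study appointments". Section 5.4 describes contacting women before appointments fall due, and three calls after a missed visit.

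The SAP names what is compared, "Changes from baseline to follow-up assessments on variables related to alcohol use and contextual/co-occurring issues (i.e., violence and depression", and tests it with a Cochran-Armitage trend test. Summaries are given overall and by enrolment while pregnant or postpartum. The SAP names no analysis set, denominator or rule for a missing assessment of any kind.

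Sections 7.1.1 to 7.2 deal with safety. Stillbirth and miscarriage are named as SAEs, and SAEs are reported whether or not they are related to the study. On attrition: "We will monitor attrition rates for participants but drop out from the study will not be reported as an AE", unless it is tied to an untoward event of participation.

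**The concern.** Ordinary missed visits trigger calls, while a loss ends them. The missing data would therefore be triggered by an event that may itself be related to drinking and to later depression, and depression is one of the outcomes compared. The Cochran-Armitage test compares proportions between groups and does not pair a woman with her own baseline. If baseline used all enrolled women and follow-up only those assessed, a proportion could move although no woman had changed. If the tables did not separate losses from other gaps, a reader could not see this.

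There also seemed to be tension with section 7.2, which says "SAEs will be systematically assessed by staff at each participant contact as well as at each scheduled follow-up" and, for a woman who withdraws or is discontinued because of an SAE, that "the participant will be monitored by the investigator via ongoing status assessment until (1) a resolution is reached".

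**Working it through.** The plan gives no loss rate, attrition rate, prevalence or power figure, so there is nothing of its own to reproduce. The planned size, 60 women (30 pregnant, 30 postpartum), is from the introduction to Protocol Chapter 5. All other inputs below are assumptions.

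**1. What the rule does.** It stops pursuit of appointments. It does not cancel the assessments or turn away a woman who attends. That later data will usually be missing is a reasonable inference, not a stated rule.

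**2. Bounds on a follow-up proportion.** Let E be the number enrolled, L missing after a loss and M missing for other reasons. Scoring all missing women positive and then all negative gives a range of (L + M)/E, of which L/E is due to losses.

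| E | L | M | Range (points) | Due to losses (points) |
|---|---|---|---|---|
| 30 | 1 | 0 | 1/30 = 3.3 | 3.3 |
| 30 | 3 | 0 | 3/30 = 10.0 | 10.0 |
| 60 | 1 | 0 | 1/60 = 1.7 | 1.7 |
| 60 | 3 | 0 | 3/60 = 5.0 | 5.0 |
| 30 | 1 | 3 to 6 | 4/30 to 7/30 = 13.3 to 23.3 | 3.3 |
| 30 | 3 | 3 to 6 | 6/30 to 9/30 = 20.0 to 30.0 | 10.0 |

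With one loss and 3 to 6 other gaps, the loss accounts for 1/4 to 1/7 of the range.

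**3. Shift from change of sample alone.** With baseline prevalence q in all E women and qL in the women with losses, the prevalence in those who remain is (Eq − L·qL)/(E − L). Take E = 30 and q = 20%, 40% and 60%:

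- L = 1, qL = 1: −2.8, −2.1, −1.4 points. With qL = 0: +0.7, +1.4, +2.1.
- L = 3, qL = 1: −8.9, −6.7, −4.4 points (for example, 6/30 = 20.0% becomes 3/27 = 11.1%). With qL = 0: +2.2, +4.4, +6.7.

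The larger figures need 3 losses in 30 (10%), with all three women alike at baseline. If baseline is shown for the same women who are assessed, this shift is zero by construction (3/27 against 3/27).

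**4. Scale, like for like.** The 95% Wald half-width at n = 30 is 1.96·√(p(1 − p)/30): 16.4 points at p = 0.3 or 0.7 and 17.9 at p = 0.5. Full widths are 2 × 16.4 = 32.8 and 2 × 17.9 = 35.8. The bounds in step 2 are full ranges, so 3.3 to 10.0 (with M = 0) compares with 32.8 to 35.8. The signed shifts in step 3 compare with the half-width. At p = 0.2 that is 1.96·√(0.16/30) = 14.3, against the extreme of −8.9.

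**5. Which outcomes are open to it.** Under section 5.2 a woman must "test positive for alcohol use by urinalysis (i.e., EtG", and Table 1 there lists a negative EtG among the reasons for not taking part. The baseline EtG proportion is 100% whoever is later removed, so step 3 can apply only to violence, depression and amount of drinking.

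**6. Whether losses can be separated from other gaps.** A loss reaches the Project Coordinator (5.4), there is a form for fetal, birth and neonatal outcomes (5.6.1), and stillbirth and miscarriage are SAEs (7.1.2, 7.2). The counts can be tabulated from data already collected.

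**7. Sections 5.4 and 7.2.** One ends the chasing of appointments. The other concerns safety status at contacts that do occur, and after an SAE-related withdrawal or discontinuation. Neither negates the other, so no contradiction is shown.

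**The case for a change.** The best case for amending the SAP is that the event is foreseen and the remedy cheap. Stillbirth and miscarriage are named in advance. At assumed risks of 2%, 5% and 10%, the chance of at least one loss among 30 women is 1 − 0.98^30 = 0.455, 1 − 0.95^30 = 0.785 and 1 − 0.90^30 = 0.958. The named test does not use pairing, so nothing in the SAP forces a same-women comparison. Counts by visit and stratum, with one further baseline column, would need no visits and no contact with bereaved women.

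Much of this stands. The SAP is silent, the missingness may well be informative, and a table of women enrolled, assessed, not assessed after a loss and not assessed for other reasons is good reporting. But the silence covers every missed assessment, including those after withdrawal, and losses are only one part of it. The table can be produced at analysis from existing records. Scoring missing alcohol data both ways would add little, because drinking after a loss is not exposure in pregnancy or lactation and it would be unclear what was being bounded.

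**Conclusion.** No change follows. The stop on tracking is a fair trade-off between complete data and the burden on bereaved women, and what the SAP leaves unsaid here is reporting detail that an analyst would supply: denominators by visit and stratum, losses shown apart from other gaps, and baseline values for the women assessed. Under assumed counts of 1 to 3 losses per 30 women, the undetermined range is 3.3 to 10 points in a stratum. The shift from change of sample is −2.8 to +2.1 points for one loss and −8.9 to +6.7 at the extremes for three, at assumed baseline prevalences of 20% to 60%. The direction is unknown, and the size is below sampling error in a 60-woman, largely descriptive pilot.

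This rests on losses being recorded as the Protocol describes. It also takes as given, without support in the documents, that a loss usually leads to a missing assessment and that it is related to drinking or depression. If either fails, the effect is smaller still. Many more losses than assumed would call for more caution in reading the follow-up tables.
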